1.0 Summary of Study

Background: Total hip arthroplasty (THA) is now the second most common joint replacement surgery in the US due in part to an aging population [1]. Opioid sparing analgesic treatments such as lumbar plexus and femoral nerve blocks are effective but they carry a high risk of undesirable lower limb motor or muscle weakness. Fascia iliaca block, on the other hand, does not consistently provide adequate pain relief [2, 3]. Today, early mobilization, rehabilitation and participation in physical therapy is an integral part of enhanced functional recovery program after THA. Because innervation of the hip joint is complex and preservation of lower extremity motor function is paramount, optimal regional analgesic intervention for THA has yet to be defined [4, 5]. The pericapsular nerve group (PENG) block is a novel regional anesthesia technique for providing analgesia after hip fractures and hip arthroplasties. Quality of recovery scores are patient reported outcome measures evaluating recovery after surgery and anesthesia. The quality of recovery-15 (QoR-15) is a validated questionnaire to assess postoperative recovery (6). The aim of this single center, double blind, randomized controlled trial is to confirm the efficacy of the PENG block for postoperative recovery after primary THA.

Methods: The participants will be randomly assigned to either PENG block group or “no Block” group using a random number generator. The patient will be blinded to the group allocated. The primary outcome will be the quality of recovery 15 score (QoR-15). The secondary outcomes will be visual analog scale score of pain postoperatively, opioid

requirements in first 24 hours, ambulation distance on postoperative day1 and patient satisfaction. Statistical analysis will be performed using the student's t-test, Mann-Whitney U test, and Fisher's exact test as appropriate per sample. A p-value of less than 0.05 will be considered statistically significant.

INTRODUCTION

2.0 Background and Rationale

As the practice of anesthesiology has grown increasingly safe, the focus has shifted to improving quality, as evidenced by the robust spread of Enhanced Recovery after Surgery protocols. The implications from poor quality recovery is vast, including prolonged stay in the recovery room or hospital [7]. The Quality of Recovery (QoR-15) questionnaire is a method to measure five dimensions using 15 questions: physical independence, pain, comfort, patient support, emotional state [8]. It is an extensively validated measure of patient-assessed quality of recovery after surgery, having been demonstrated over a variety of clinical settings. QoR-15 scores range from 0 (extremely poor quality of recovery) to 150 (excellent). Mean time to complete the 15-question survey is 3 minutes, a marker of its clinical utility [9]. As we aim to improve our perioperative care and develop approaches to improve medicine in this regard, the QoR-15 provides a useful tool.

The effective postoperative analgesia is vital as acute surgical pain is a potential risk factor for future chronic pain. Persistent pain after THA (more than three months) is reported in 27% of patients and is reported to be correlated with the intensity of early postoperative pain

rather than preoperative pain levels [10,11]. Utilizing regional anesthesia helps to limit the use of opioids, however, which technique is best has yet to be determined. The lumbar plexus blocks, lumbar epidurals, and femoral nerve blocks have been associated with motor weakness. Fascia iliaca compartment block (FICB) has not been found to predictably decrease pain intensity or opioid use [12]. Quadratus lumborum (QL) block is a relatively new regional block found to provide effective analgesia after primary THA, but it can indirectly block lumbar plexus branches and may cause some motor weakness [13]. It is also a deep block and therefore contraindicated in patients on anticoagulation [14].

Recent anatomic studies by Short et al. confirmed the innervation of the anterior capsule of hip joint to be the obturator nerve, accessory obturator nerve, and femoral nerve. These studies also evaluated the relationship with these nerves and other bony or soft tissue landmarks visible by ultrasound guidance [15]. Previous studies have found histologically that the anterior capsule has predominantly nociceptive fibers, while the posterior capsule is largely made up of mechanoreceptors [16]. The pericapsular nerve group (PENG) block was introduced to target and block these articular branches providing innervation to the hip. This regional anesthetic technique was described in 2018 by Giron-Arango et al. for acute analgesia related to hip fractures [17]. Given the case reports showing the efficacy of PENG blocks for hip fracture surgeries, we sought to investigate the analgesic efficacy of PENG blocks for primary and revision THAs. The PENG block targets only the sensory branches and not the posterior mechanoreceptors; there is a potential motor-sparing effect which is desirable for early ambulation, better physical therapy, and earlier discharge. The effective analgesia and early ambulation provided by such regional anesthesia block may have positive impact on patient's mood, sleep, appetite and overall feeling of well-being. A similar postoperative recovery study

protocol has been proposed for anterior quadratus lumborum blocks for THA (18). It remains unclear whether PENG block provides sufficient analgesia and improves the quality of post-operative recovery after primary THA.

The ideal regional anesthesia technique for THA will provide adequate postoperative analgesia, reduced opioid requirements, early ambulation and physical independence. The aim of this single center, double blind RCT is to confirm the efficacy of PENG block for postoperative recovery with respect to parameters mentioned above.

3.0 OBJECTIVE(S) & HYPOTHESIS

The objectives of the study are as follows:

1. Determine the efficacy of PENG for primary THA compared to no peripheral nerve block on Quality of Recovery (QoR) after surgery.
2. Determine the efficacy of PENG for analgesia, post-operative mobilization, side effects, patient satisfaction and length of hospital stay for THA compared to no peripheral nerve block

We hypothesize that patients receiving PENG prior to primary THA will have superior quality of recovery, compared to the patients who do not receive PENG block.

Trial design: This randomized-controlled, double-blind, single-center, pragmatic, superiority trial with the two-parallel group (1:1 allocation) is designed to assess the efficacy of PENG block compared to no-block in improving the QOR for patients undergoing primary THR. The unit of randomization will be individuals (not clusters). The QOR-15 questionnaire was chosen as a measure of efficacy because it is an extensively validated measure of patient-assessed quality of recovery after surgery, having been demonstrated over a variety of clinical settings. Allocation ratio of 1:1 would allow the research question with a minimal number of subjects.

METHODS

Study setting: The study will be conducted at UAB Highlands Hospital.

4.0 INCLUSION & EXCLUSION CRITERIA

Inclusion criteria:

1. Patients undergoing primary total hip arthroplasty
2. Adults 18 years of age and older
3. Patients with an American Society of Anesthesiology (ASA) physical status classification of I, II or III
4. Primary THA

Exclusion criteria:

1. Patients with ASA physical status classification 4 or above
2. Patients with allergies/intolerances to local anesthetic
3. Patients with pre-existing neurologic or anatomic deficits in the lower extremity on the side of the surgical site
4. Patients on chronic opioid use or opioid tolerant (The FDA defines a **patient** as **opioid tolerant** if for at least 1 week he or she has been receiving oral morphine 60 mg/day; transdermal fentanyl 25 mcg/hour; oral oxycodone 30 mg/day; oral hydromorphone 8 mg/day; oral oxymorphone 25 mg/day; or an equianalgesic dose of any other **opioid**)
5. Poor understanding of English language.
6. Patients with coexisting coagulopathy
7. Patients that are pharmacologically anticoagulated will be excluded if placement of peripheral nerve block would be contraindicated according to ASRA (American Society for Regional Anesthesia) guidelines

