 - After the PENG block is placed, patients will have THA under spinal or general anesthesia. Spinal anesthesia will be provided by intrathecal injection of hyperbaric (0.75%) bupivacaine. General anesthesia will be provided by propofol induction, rocuronium for muscle relaxation and inhalation anesthetics for maintenance. Patients will receive fentanyl 25-50 mcg iv for increase in systolic blood pressure (SBP) > 25% of baseline SBP. Intraoperatively patients will also receive 4mg dexamethasone iv and 4 mg ondansetron iv.
 - Control group participants will be transferred to the block area preoperatively, and care will proceed as if they were receiving injection.
 - Patients will be placed in the supine position resting comfortably. Standard noninvasive monitors will be applied, and oxygen will be administered via nasal cannula. Parenteral midazolam and fentanyl will be titrated to patient comfort. Standard skin sterilization, prepping and draping will be applied to the area. The ultrasound probe will be used to

identify the iliopubic eminence (IPE). Only skin will be numbed using 2-3 cc of 2% lidocaine and NO bolus of bupivacaine will be injected.

- Postoperative patients in both the PENG arm and the control arm will be given scheduled PO acetaminophen 975 mg BID, and celecoxib 200mg BID (Dose of celecoxib will be adjusted based on renal function, and no celecoxib will be given for GFR < 30 ml/min) as part of multimodal pain regimen. Patients will be given a standard pain regimen of PRN Oxycodone 5 mg Q 4 hours for breakthrough pain, and hydromorphone 1mg IV every 6 hours prn as rescue analgesia for severe pain (NRS score more than 7/10). Patients will get prn ondansetron 4 mg iv every 4 hours. Naloxone iv prn will be used for any opioid related itching or respiratory depression.
- The following data will be collected
 - Quality of recovery (QoR) survey will be filled on post-operative day at 24 and 48 hours.
 - Patients will be evaluated immediately post-operatively in PACU, and 6, 12 and 24 hours post-surgery to determine VAS pain scores at rest and movement on the scale of 0-10. Also highest pain score during first 24 hours will be recorded.
 - Twenty-four hour opioid consumption will be calculated with respect to 24 hours oxycodone use and 24 hours hydromorphone use.
 - Data for postoperative use of ondansetron and naloxone will be collected. Also any postoperative episodes of nausea, vomiting, and itching will also be recorded.

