 - Patient will be followed up until nerve block resolves.
 - Patients' participation in physical therapy will be recorded from physical therapy notes. Specifically, independence in mobility and transfers (independently, with minimal supervision, with moderate supervision, with maximal supervision) and ambulation distance will be recorded using standard PT protocols used at UAB Highlands.
 - The patients will be surveyed regarding their satisfaction with postoperative analgesia. Likert scale will be used to assess their satisfaction level. There will be 4 options to report: very unsatisfied, unsatisfied, satisfied, and very satisfied.
 - The hours from block placement until hospital discharge will be calculated.
- A blinded research associate will evaluate the patients postoperatively to collect data.

Procedure	Length of Time Required of Participants	Frequency of Repetition
Presurgical Evaluation on the day of surgery	30 minutes	once
Randomization on day of surgery	5 minutes	Once
Placement of block	Approximately 30 min.	Once
Post Anesthesia Care Unit (PACU) assessment	10 minutes	Once
First postoperative assessment survey (approximately 24 hours after surgery)	20 minutes	Once

Second postoperative assessment survey (approximately 48 hours after surgery)	10 minutes	Once
--	-------------------	-------------

- Measured Outcomes:

- Primary outcome:
 - Quality of Recovery after surgery assessed on postoperative day 1 (at 24 hours).
QoR-15 scale (form attached) will be used to assess post-operative recovery based on 15 questions: scores will range from 0-150, 0 being the worst recovery and 150 being the best (excellent) recovery.
- Secondary outcomes:
 - QoR-15 at 48 hours
 - VAS scores (0-10) at immediate postoperatively, 6, 12 and 24 hours at rest and movement. VAS score 0 indicates “no pain” and 10 indicates “worst pain experienced”. Highest pain score in first 24 hours will be recorded.
 - Opioid consumption intraoperatively, as well as at 24 hours postoperatively. Oxycodone PO and Hydromorphone iv usage in first 24 hours postoperatively.
 - Incidence of nausea, vomiting and itching in first 24 hours postoperatively.
 - Physical therapist assessment of independence in mobility and transfers (independent, with minimal supervision, with moderate supervision, with maximal supervision)

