5. BMI
6. Surgical approach
7. ASA physical status
8. Average amount of opioids consumed daily in the week prior to surgery
9. VAS scores immediately postoperatively in the recovery room, 24 hours postoperatively
10. Opioid consumption intraoperatively and postoperatively
11. Physical therapy assessments
 1. Degree of independence in mobility and transfers at 24 hours
 2. Ambulation distance at 24 hours
12. Time to discharge from the hospital

Projected Overall Study Timeline

Date	Study Start-Up	Enrollment	Data Entry and Analysis	Study Write-Up
12 2020	X			
01 2021		X		
04 2021			X	
05 2021				X

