9.0 STATISTICAL CONSIDERATIONS

General Data Analysis Plan:

The distribution of the continuous factors will be examined using data visualization techniques such as q-q plots and the Shapiro-Wilk test. All normally distributed demographic and continuous variables will be expressed as means and standard deviations; categorical factors will be expressed as proportions. For non-normal data, the medians and inter quartile ranges will be displayed. For data that are normally distributed, Student's t-test will be used to compare the groups. For data that are not normally distributed, a Mann-Whitney tests will be used for comparisons. Chi-square or Fisher's exact tests will be used to analyze categorical data. Time to event data such as distance of first ambulation will be analyzed using Kaplan-Meier curves. The planned sub-group analysis will be conducted for GA vs. Spinal using a 2x2 ANOVA test. For all comparisons, a value of $p < 0.05$ will be considered statistically significant. Statistical analyses will be performed using SAS for Windows, version 9.2.

Statistical Power and Sample Size Estimates: Fifty-six patients in each group are required to detect a Minimal Clinically Important Difference (MCID) of 8 points for QoR-15 score assuming a standard deviation of 15 points using data from previous studies (19, 20) for 5% significance level and 80% power.

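### Pre-operative opioid dose is collected but used in no analysis, so the 24-hour opioid comparison gives up some precision (minor)

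*Combined protocol and SAP*

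**What the plan says.** - **Eligibility.** Section 4.0, exclusion 4, names two groups: "Patients on chronic opioid use or opioid tolerant". The parenthesis that follows defines tolerance only, as a patient who "for at least 1 week he or she has been receiving oral morphine 60 mg/day; transdermal fentanyl 25 mcg/hour; oral oxycodone 30 mg/day", or an equivalent. Chronic use is given no dose and no duration.
- **Baseline data.** Section 6.0, list of variables, item 8: "Average amount of opioids consumed daily in the week prior to surgery".
- **Post-operative orders.** Section 6.0 gives both arms "PRN Oxycodone 5 mg Q 4 hours for breakthrough pain" and "hydromorphone 1mg IV every 6 hours prn as rescue analgesia for severe pain".
- **Outcome.** Section 6.0 lists as a secondary outcome "Oxycodone PO and Hydromorphone iv usage in first 24 hours postoperatively", and the data-collection text says "Twenty-four hour opioid consumption will be calculated with respect to 24 hours oxycodone use and 24 hours hydromorphone use".
- **Analysis.** Section 9.0 uses Student's t-test for normally distributed data; otherwise "For data that are not normally distributed, a Mann-Whitney tests will be used for comparisons". Its only two-factor analysis is a 2x2 ANOVA for general versus spinal anesthesia. The appended statistical section describes two-sample t-tests, Wilcoxon rank sum tests and chi-square tests. Neither section names a covariate.
- **Randomization.** Section 5.0 describes permuted blocks of variable size and names no stratification factor.

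**The concern.** A patient's opioid dose before surgery is a plausible predictor of opioid use in the day after it. The plan records that dose and then leaves it out of the comparison where it would help most. Variation between patients that could be explained stays in the error term, and the interval for the arm difference is wider than it needs to be. Because randomization is not stratified on prior use, the arms may also differ by chance in their number of users, and an unadjusted estimate moves with that difference.

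Reduced opioid requirement is one of the effects that section 2.0 wants from the block, so a sharper estimate has some value. The outcome is secondary, however, and no sample size is attached to it.

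**Working it through.** **1. The plan's own figure.** The only powered outcome is QoR-15 (section 9.0: difference 8, SD 15, 5% significance, 80% power). Taking two sides, n = 2 x (1.960 + 0.842)^2 x 15^2 / 8^2 = 55.2, so 56 per group. The stated 56 is reproduced, and this point does not affect it.

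**2. Limits on the outcome (section 6.0).** Oxycodone: 24/4 x 5 mg = 30 mg in 24 h. Hydromorphone: 24/6 x 1 mg = 4 mg IV in 24 h, given in addition. The 30 mg limit therefore applies to one component, not to total opioid.

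**3. Validity of the unadjusted test.** Simulated with 56 per arm, 20% users, a 10 mg shift in users and no treatment effect, the unadjusted t-test rejected in 4.8% of trials. The type I error is kept.

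**4. Chance imbalance.** The standard error of the difference in user share is sqrt(2p(1-p)/56), where p is the assumed user share.
- p = 10%: 0.057, so a 95% range of about +/-11 percentage points.
- p = 20%: 0.076, so about +/-15 percentage points.

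**5. Gain from adjustment in general terms.** If prior dose has correlation rho with 24-hour use, adjustment multiplies the variance by 1 - rho^2. At rho = 0.2 the cut is 4%; at 0.4, 16%; at 0.6, 36%. The documents give no rho.

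**6. Gain with the oxycodone limit modelled.** All inputs here are assumptions except 56 per arm, the 5 mg step and the 30 mg limit.
- Non-users average 15 mg oxycodone in 24 h, with residual SD 8.
- Users enter at 5-29 mg/day, spread uniformly.
- Each pre-operative mg adds b mg after surgery, with b = 0.5 to 1.0.
- Doses are rounded to 5 mg and limited to 30 mg; 4,000 trials per setting.

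Without the limit the gain can be checked by hand. The variance of prior dose is V = p(17^2 + 24^2/12) - (17p)^2, which is 30.8 at p = 10%. The cut is b^2V/(b^2V + 64): 7.7/71.7 = 11% at b = 0.5 and 30.8/94.8 = 32% at b = 1.0.

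With the limit, the simulated cut in the variance of the arm difference is smaller:

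| Assumed user share | Slope b | Variance cut |
|---|---|---|
| 5% | 0.25-1.0 | about 0-11% |
| 10% | 0.5-1.0 | about 7-18% |
| 20% | 0.5-1.0 | about 14-31% |

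The ends of these ranges vary by a few points between simulation runs. As interval width, a cut of 7% gives sqrt(0.93) = 0.96 and a cut of 31% gives sqrt(0.69) = 0.83, so intervals about 4% to 17% narrower. Hydromorphone use was not simulated.

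**The case against.** The strongest reply is that an unadjusted comparison is a legitimate plan. It is unbiased under randomization, its p-value and interval already allow for chance imbalance, and the outcome is one of many unpowered secondaries. All of this stands, and it is why the point is minor.

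It can also be said that few users will enrol. The parenthesis in exclusion 4 is attached to tolerance, so the plain reading removes chronic users as a separate group; applying the threshold to both terms would make the first redundant. Item 8 may be an eligibility check or a baseline descriptor, since its one-week window matches the one in exclusion 4. This stands in part. Short-term or occasional users are eligible on either reading, and the missing definition of chronic use leaves some sub-threshold users to the screener's judgement. The documents do not say how many there will be.

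A reader might go further and infer three things that the documents do not support.
- **That the trial knowingly admits daily users up to the tolerance threshold.** The plain reading is against it, and a patient at 30 mg/day oxycodone for a week meets the tolerance definition and is excluded.
- **That, because the oxycodone threshold and the 24-hour oxycodone limit are both 30 mg, users have almost no room to show a block effect.** The limit leaves out hydromorphone, and the argument needs as-needed oxycodone to replace home opioids. The documents do not say whether home opioids continue.
- **That imbalance in users could create a false PENG effect beyond ordinary sampling error.** The 4.8% type I error shows otherwise.

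**Conclusion.** The point holds as a modest loss of efficiency. A baseline variable that is already collected is left out of the comparison that it is most likely to sharpen. The test that is planned remains valid. The primary outcome and its sample size are unaffected.

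The size rests on the assumed user share, slope and residual SD. With the oxycodone limit modelled and slopes of 0.5-1.0, the variance cut is roughly 7-18% at 10% users and 14-31% at 20%. Figures that ignore the limit overstate the gain and should not be used. At 5% users the gain may be close to nothing, and with no users it is zero. Severity is minor.

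The two terms in exclusion 4 are a secondary matter: a missing definition that should be settled, not evidence that chronic users are enrolled.

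**What to change.** **Section 9.0.** Prespecify that the 24-hour oxycodone and 24-hour hydromorphone comparisons are each adjusted for item 8. Use ANCOVA, or rank ANCOVA where skew or the dose limit makes a linear model doubtful. Keep the unadjusted t-test or Mann-Whitney test as a sensitivity analysis. State that non-users are entered as zero and that prior doses of different opioids are put on one scale, because item 8 names no unit. The appended statistical section should say the same. It is written in the past tense; if the comparison has already been made, the adjusted result should be labelled as supplementary.

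**Section 4.0.** Reconcile the two terms in exclusion 4 so that the criterion has one reading. The definition is for the sponsor to choose; none is proposed here.

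**Cost.** A few sentences and no new data. The model gains one term whose covariate will be zero for most patients, and linear adjustment does not undo the oxycodone limit where it binds. If few users enrol, the gain is small.

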5.0 RANDOMIZATION/RECRUITMENT DETAILS (If applicable)

- Randomization groups, how will subjects be randomized:

Upon enrollment in the study, participants will be randomized 1:1 to either the investigational group (“PENG Block” group) or the control group (“No Block” group). Participants will be randomized using a random number generator. The randomization will be performed using computer-generated random numbers. The study will follow a 1:1 allocation ratio for the intervention (PENG) and control (No-PENG). A random permuted block will be used to reduce the predictability of allocation. The randomization sequence will be generated using computer software using a block randomization method where blocks are variable in size (minimum block size four). The study will use a sealed opaque envelope as method to comply with allocation concealment.

- Blinded Yes No (Single Double please check box).
- Participants and outcome assessors will be blinded. The anesthesiologist performing the block will not be blinded to the group allocation.

6.0 **STUDY INTERVENTIONS/PROCEDURES**

All patients will receive standard pre-operative dose of 1000 mg of acetaminophen, and 200 mg of celecoxib as multimodal analgesia regimen.

- Study design:[Click here to enter text.](#)
 - Participants in the study will be blinded to their treatment group. All patients will receive acetaminophen 975 mg PO and celecoxib 200 mg PO. Dose of celecoxib will be adjusted based on renal function, and no celecoxib will be given for GFR < 30 ml/min.
 - Participants in the pericapsular nerve group block (PENG) arm will receive a PENG block preoperatively in the block area placed under direct ultrasound guidance as follows:
 - Patients will be placed in the supine position resting comfortably. Standard noninvasive monitors will be applied, and oxygen will be administered via nasal cannula. Parenteral midazolam and fentanyl will be titrated to patient comfort. Standard skin sterilization, prepping and draping will be applied to the area. Anatomical landmarks identified using ultrasound and skin will be numbed using 2-3 cc of 2% lidocaine. Long acting local anesthetic, a bolus of 25 cc of 0.5 % Bupivacaine will be injected lateral to iliopubic eminence (IPE). A Curvilinear low frequency (2-5 MHz) ultrasound probe will be used to identify landmarks. A 22 G, 10 cm needle will be inserted using in-plane technique and advanced to target site (17).
 - After the PENG block is placed, patients will have THA under spinal or general anesthesia. Spinal anesthesia will be provided by intrathecal injection of hyperbaric (0.75%) bupivacaine. General anesthesia will be provided by propofol induction, rocuronium for muscle relaxation and inhalation anesthetics for maintenance. Patients will receive fentanyl 25-50 mcg iv for increase in systolic blood pressure (SBP) > 25% of baseline SBP. Intraoperatively patients will also receive 4mg dexamethasone iv and 4 mg ondansetron iv.
 - Control group participants will be transferred to the block area preoperatively, and care will proceed as if they were receiving injection.
 - Patients will be placed in the supine position resting comfortably. Standard noninvasive monitors will be applied, and oxygen will be administered via nasal cannula. Parenteral midazolam and fentanyl will be titrated to patient comfort. Standard skin sterilization, prepping and draping will be applied to the area. The ultrasound probe will be used to

identify the iliopubic eminence (IPE). Only skin will be numbed using 2-3 cc of 2% lidocaine and NO bolus of bupivacaine will be injected.

- Postoperative patients in both the PENG arm and the control arm will be given scheduled PO acetaminophen 975 mg BID, and celecoxib 200mg BID (Dose of celecoxib will be adjusted based on renal function, and no celecoxib will be given for GFR < 30 ml/min) as part of multimodal pain regimen. Patients will be given a standard pain regimen of PRN Oxycodone 5 mg Q 4 hours for breakthrough pain, and hydromorphone 1mg IV every 6 hours prn as rescue analgesia for severe pain (NRS score more than 7/10). Patients will get prn ondansetron 4 mg iv every 4 hours. Naloxone iv prn will be used for any opioid related itching or respiratory depression.
- The following data will be collected
 - Quality of recovery (QoR) survey will be filled on post-operative day at 24 and 48 hours.
 - Patients will be evaluated immediately post-operatively in PACU, and 6, 12 and 24 hours post-surgery to determine VAS pain scores at rest and movement on the scale of 0-10. Also highest pain score during first 24 hours will be recorded.
 - Twenty-four hour opioid consumption will be calculated with respect to 24 hours oxycodone use and 24 hours hydromorphone use.
 - Data for postoperative use of ondansetron and naloxone will be collected. Also any postoperative episodes of nausea, vomiting, and itching will also be recorded.
 - Patient will be followed up until nerve block resolves.
 - Patients' participation in physical therapy will be recorded from physical therapy notes. Specifically, independence in mobility and transfers (independently, with minimal supervision, with moderate supervision, with maximal supervision) and ambulation distance will be recorded using standard PT protocols used at UAB Highlands.
 - The patients will be surveyed regarding their satisfaction with postoperative analgesia. Likert scale will be used to assess their satisfaction level. There will be 4 options to report: very unsatisfied, unsatisfied, satisfied, and very satisfied.
 - The hours from block placement until hospital discharge will be calculated.
- A blinded research associate will evaluate the patients postoperatively to collect data.

Procedure	Length of Time Required of Participants	Frequency of Repetition
Presurgical Evaluation on the day of surgery	30 minutes	once
Randomization on day of surgery	5 minutes	Once
Placement of block	Approximately 30 min.	Once
Post Anesthesia Care Unit (PACU) assessment	10 minutes	Once
First postoperative assessment survey (approximately 24 hours after surgery)	20 minutes	Once

Second postoperative assessment survey (approximately 48 hours after surgery)	10 minutes	Once
--	-------------------	-------------

- Measured Outcomes:

- Primary outcome:
 - Quality of Recovery after surgery assessed on postoperative day 1 (at 24 hours).
QoR-15 scale (form attached) will be used to assess post-operative recovery based on 15 questions: scores will range from 0-150, 0 being the worst recovery and 150 being the best (excellent) recovery.
- Secondary outcomes:
 - QoR-15 at 48 hours
 - VAS scores (0-10) at immediate postoperatively, 6, 12 and 24 hours at rest and movement. VAS score 0 indicates “no pain” and 10 indicates “worst pain experienced”. Highest pain score in first 24 hours will be recorded.
 - Opioid consumption intraoperatively, as well as at 24 hours postoperatively. Oxycodone PO and Hydromorphone iv usage in first 24 hours postoperatively.
 - Incidence of nausea, vomiting and itching in first 24 hours postoperatively.
 - Physical therapist assessment of independence in mobility and transfers (independent, with minimal supervision, with moderate supervision, with maximal supervision)
 - Physical therapist documentation of ambulation distance
 - Patient satisfaction on Likert scale will be used to assess their satisfaction level. There will be 4 options to report: very unsatisfied, unsatisfied, satisfied, and very satisfied.
 - Hours to hospital discharge (Surgery finish time to discharge time).

List of variables/data points you will be collecting (e.g. – age, gender, date of surgery, etc.):

We will collect the following data:

1. patient age
2. patient gender

3. Weight
4. Height

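### GA versus spinal is the only planned subgroup factor, but it is not fixed before randomisation, stratified on, adjusted for or listed as data, so the plan forgoes a small possible gain and leaves the subgroup open to a post-randomisation choice

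*Combined protocol and SAP*

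**What the plan says.** **Allocation (Section 5.0).** Assignment is 1:1 in permuted blocks of varying size, with sealed envelopes: "A random permuted block will be used to reduce the predictability of allocation". No stratification factor is named. Participants and outcome assessors are blinded; the anaesthesiologist who performs the block is not.

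**Anaesthetic (Section 6.0).** The procedures table puts randomisation on the day of surgery. The text then says "After the PENG block is placed, patients will have THA under spinal or general anesthesia". It does not say how the type is chosen, by whom, or when.

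**Data (Section 6.0).** The bulleted data items, the outcomes and the 12-item list introduced by "We will collect the following data" do not name anaesthetic type. Surgical approach is listed, but that is a different variable. Intraoperative opioid use is collected.

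**Analysis (Section 9.0).** Groups are compared by t-test, or Mann-Whitney if not normal. One subgroup is named: "The planned sub-group analysis will be conducted for GA vs. Spinal using a 2x2 ANOVA test". The sample-size aim is: "detect a Minimal Clinically Important Difference (MCID) of 8 points for QoR-15 score". The stated number is 56 per arm, with an SD of 15, a 5% level and power of 80%.

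**Closing Statistical analysis section (after the QoR-15 form).** Written in the past tense, it describes two-group tests only, with no subgroup analysis and no ANOVA.

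**The concern.** The plan treats the anaesthetic as important enough to be its only subgroup factor, but makes no use of it in allocation or in the primary comparison. If it is related to first-day QoR-15, adjusting for it would remove some residual variance at almost no cost.

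Timing matters more for interpretation. A subgroup factor should be a baseline characteristic. Here the anaesthetic is given after randomisation and after an unblinded block, and the documents do not say the type was settled earlier. If it was not, the GA and spinal subgroups may not be comparable between arms, and an analysis split or adjusted on anaesthetic received conditions on something that could have been influenced by allocation.

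**Working it through.** **1. The plan's own figure.** Inputs from Section 9.0: difference 8, SD 15, 5% significance, 80% power. Sidedness is not stated.

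- Two-sided, normal approximation: n = 2 × [15 × (1.960 + 0.842) / 8]² = 55.19, so 56 per arm. The stated figure reproduces. A one-sided test would give 44.
- Noncentral t power at 56 per arm: noncentrality = 8 / (15 × √(2/56)) = 8 / 2.835 = 2.822 on 110 df, giving 79.9%.

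The SD of 15 is for all patients and is not specific to one anaesthetic. Any GA-spinal variation is already inside it.

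**2. Gain from putting the factor in the model.** Two inputs are assumptions, because the documents give neither: the share p with the less common anaesthetic (10% to 50%) and the GA-spinal gap g in QoR-15 (0, 5 or 10 points).

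Share of variance explained: R² = p(1 − p)g² / 225. Residual SD = 15 × √(1 − R²). Power is then recomputed by noncentral t at 56 per arm, with the factor balanced.

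| p | g | R² | Residual SD | Power | Gain over 79.9% (points) |
|---|---|---|---|---|---|
| any | 0 | 0 | 15.00 | 79.9% | nil |
| 10% | 5 | 0.010 | 14.92 | 80.3% | 0.4 |
| 50% | 5 | 0.028 | 14.79 | 81.0% | 1.1 |
| 10% | 10 | 0.040 | 14.70 | 81.5% | 1.6 |
| 50% | 10 | 0.111 | 14.14 | 84.3% | 4.4 |

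**3. What stratification adds once the model adjusts.** Without stratification, chance correlation between arm and factor inflates the variance of the adjusted effect by 1/(1 − ρ²). With 112 patients the average of ρ² is 1/111 = 0.009, so the inflation is about 0.9%. Most of the gain therefore comes from adjustment. The exception is the smallest case (p = 10%, g = 5), where R² is itself only 1% and the two nearly cancel.

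**4. Chance imbalance.** The SD of the difference between arms in the share is √(2p(1 − p)/56): 5.7 percentage points at p = 10% and 9.4 at p = 50%. An imbalance of 1.96 SD (11.1 to 18.5 points) would move the unadjusted difference by 0.6 to 0.9 QoR-15 points for g = 5, and by 1.1 to 1.9 for g = 10. An imbalance of one SD with g = 5 moves it by 0.3 to 0.5. These are part of the random error that the t-test already counts (standard error 2.83), not an added bias.

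**5. The interaction test.** SE = 15 × √(2/n_GA + 2/n_spinal), with per-arm counts from 5.6 and 50.4 (p = 10%) to 28 and 28 (p = 50%). This gives 9.45 down to 5.67. Power for an 8-point interaction is 13% to 29%. The interaction detectable with 80% power is 26.5 down to 15.9 points. Stratifying does not cure this.

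**The case against.** Several stronger readings are tempting, and the case against them is sound.

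- **That precision is lost or power falls below 80%.** Not supported. The overall SD already carries any GA-spinal variation, and 56 per arm reproduces. Only a possible gain is forgone.
- **That unstratified blocks make the comparison unsound.** Not supported. Unstratified randomisation is valid, and chance imbalance is within the test's error rate.
- **That the 2x2 ANOVA has no input and cannot be run.** This over-reads the lists. The 12-item list omits QoR-15 itself, and none of the lists names the treatment arm. Since intraoperative opioid use is collected, anaesthetic type could probably be taken from the same records, although the plan does not say so. The fair statement is that the field is unspecified.
- **That the anaesthetic was chosen differently by arm.** The documents do not show this. They do not say who chooses it or when. They leave the possibility open, no more.

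A 2x2 ANOVA also ordinarily yields an arm effect adjusted for anaesthetic, so the proposed model is close to one already planned; but that effect is not the designated primary comparison. It is also fair that the size rests on an assumed mix and gap, and that a 10-point gap would exceed the 8-point treatment target.

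What remains is that the plan does not fix its only subgroup factor before allocation and does not use it in the primary comparison, and that its two statistical sections differ on whether the subgroup analysis exists.

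**Conclusion.** The point holds as a low-cost improvement, not as an error that undermines the primary result. The stated 80% power stands. Under the assumed 10% to 50% share, the forgone gain is about 0.4 to 1.1 power points for a 5-point gap and 1.6 to 4.4 for a 10-point gap, and nil if the anaesthetics do not differ in QoR-15. Neither the mix nor the gap is in the documents, so confidence in the size is low.

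The more durable part needs no assumed effect size: as written, the subgroup could be defined by a choice made after randomisation, and only the intended type fixed before allocation is a safe covariate. With 13% to 29% power for an 8-point interaction, the subgroup result can only be exploratory.

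**What to change.** **If enrolment is open**

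1. Add a data field for the intended anaesthetic, completed before the envelope is opened, and a second field for the anaesthetic received.
2. Keep one sealed-envelope series per intended type, each with the same variable blocks.
3. Compare 24-hour QoR-15 with a linear model containing arm and intended anaesthetic. Keep the two-sample test as a sensitivity analysis.
4. Take the arm-by-anaesthetic interaction from the same model with that term added, and label it exploratory.
5. Reconcile Section 9.0 with the closing Statistical analysis section on whether the ANOVA is still planned.

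**If enrolment has closed**, which the past tense of the closing section suggests, steps 1 to 3 come too late. Adjust for anaesthetic received only as a labelled sensitivity analysis, and state that it is a post-randomisation variable unless records show it was fixed beforehand. Step 5 still applies.

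**Cost.** Two data fields, a second envelope series and a short SAP edit, with no extra patients. The downside is that the intended type must be named before allocation, and later switches dilute the gain.
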